6.4.2 Discharge Criteria

Subjects will be discharged from the inpatient unit on Study Day 9 if they meet the following discharge criteria:

1. Did not develop fever during the inpatient stay.
2. If fever did develop, the subject has remained afebrile for 48 hours prior to discharge.
3. Any continuing solicited AEs are Grade 2 or lower.
4. The titer of ZIKV in serum, cervico-vaginal secretions, semen, urine, or saliva, is $\leq 1.4 \times 10^6$ genomic copies/mL by Study Day 8 or has been previously demonstrated to be non-infectious at the detected titer.

Because of the low inoculum dose to be given, the low titers recovered from NHP, our experience with the dengue CHIM, and reported ZIKV literature, subjects are expected to be free of infectious transmissible virus in the serum by Day 9.

6.4.3 Mitigation Plan Should a Subject Leave the Unit Early

Potential volunteers are carefully screened prior to enrollment to ensure they understand their responsibilities and are willing and able to carry them out, including remaining in the inpatient unit until discharge criteria are met. Subjects must be willing to stay in the inpatient unit until they meet discharge criteria as an inclusion criterion. Subjects are provided with several amenities during their inpatient stay including internet access, entertainment (movies, cable television, craft projects, games, and classes. In addition, catered meals are provided to subjects while on the unit. Should a subject express a desire to leave the unit early, the PI will counsel the subject about why he or she is being asked to remain on the unit and counsel him or her to stay. However, should a subject insist upon leaving the unit prior to discharge criteria being met, the study staff will:

- Reinforce the risk of mosquito-borne & sexual transmission of ZIKV to third parties
- Review ZIKV transmission preventive measures with the volunteer

- Perform pregnancy prevention counseling
- Provide mosquito repellent containing DEET and review with volunteer how to use it. This will be done during mosquito season (May through October).
- If possible, arrange daily outpatient follow-up visits for the subject for clinical examination and to obtain scheduled blood/urine/saliva/cervico-vaginal secretion/semen samples until Study Day 9, after which point they will resume usual outpatient schedule.
- If subject cannot physically return for follow-up visits, will contact the subject by phone to inquire about adverse events and perform pregnancy prevention counseling

6.4.4 Subject Temperature Memory Card

Subjects will be provided a thermometer and a “Temperature Memory Card”, to use as a memory aid and will be asked to record temperatures 2 times a day on Study Day 9 - Study Day 16. Staff will review the temperature card on Study Days 10, 12, 14, 16, and 21 post-inoculation to assess for any fevers and compare subject recordings to the study visit temperatures. Staff will record all temperatures recorded by the subject and will also separately record the maximum temperature (T_{max}) for each date on the source document. Subject memory cards will not be collected by the study staff as subject’s recordings will not be considered required data.

Staff will instruct subjects how to use the thermometers, to take their temperatures at approximately the same times each day, and to take additional temperatures if they feel they have elevated temperatures. Subjects will be asked to wait at least 15 minutes after eating, drinking, and smoking before taking their temperatures. They will be asked to confirm an elevated temperature ($\geq 100.4^{\circ}\text{F}$) by retaking the temperature after a 20-minute interval and at 1 hour. Temperatures not documented to last at least 1 hour will not be considered an AE or included in the analysis.

6.4.5 Persistence of ZIKV in Bodily Fluids

If Zika virus is detected in any bodily fluid at Study Day 180, the subject will continue to be followed until Zika virus is no longer detected in the bodily fluid. To achieve this, the subject will be brought back for unscheduled visits for collection of the specimen of interest (the bodily fluid that was positive for Zika virus at Study Day 180) and for review of clinical symptoms. If clinical symptoms are reported, the subject will undergo clinical evaluation. Persistent shedding of Zika virus in bodily fluids at Study Day 180 will be reported to the DSMB and the FDA as soon as it is detected. The DSMB and the FDA will be asked to provide additional guidance as to follow-up procedures, the interval of specimen collection, and the duration of specimen collection.

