4.1 Inclusion Criteria

All of the following criteria must be fulfilled for a subject to qualify for inclusion in this study:

1. Adult ZIKV or DENV-naïve male and non-pregnant females 18 – 40 years of age, inclusive.
2. Good general health as determined by physical examination, laboratory screening, and review of medical history.
3. Available for the duration of the study, approximately 26 weeks post-inoculation.
4. Must be able to complete the informed consent process and comprehension assessment independently and without assistance.
5. Willingness to participate in the study as evidenced by signing the informed consent document.
6. Willingness to reside in the inpatient unit for 9 days (or longer for safety if necessary) following receipt of ZIKV or placebo.
7. Male subjects: Willingness to use barrier contraception during cervico-vaginal, anal, and oral intercourse through Study Day 90 (in accordance with CDC guidance).
8. Female subjects: Willingness to use barrier contraception during cervico-vaginal, anal, and oral intercourse through Study Day 56 (in accordance with CDC guidance).
9. Female subjects of childbearing potential must be willing to use effective contraception while at risk of Zika infection. We will follow CDC guidelines for the use of effective contraception of 8 weeks post-infection; time of infection is defined as inoculation with challenge virus. Reliable methods of contraception include: hormonal birth control* (implantable, hormonal patch, hormonal vaginal ring, oral contraception, Depo-Provera injection, etc.), surgical sterilization (hysterectomy, tubal ligation, or tubal coil at least 3 months prior to inoculation), and intrauterine device. All female subjects will be considered having child-bearing potential except for those with post-menopausal status documented as at least 1 year since last menstrual period and females who have sex with females (exclusively) and have no intention of conceiving a child during the study. Females who are not considered to be of childbearing potential will not be required to use contraception other than barrier contraception for the purpose of reducing potential transmission.

*Volunteers on hormonal birth control must not be on medications or other agents that decrease the effectiveness of hormonal birth control.

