3. Perform serum β -HCG testing (females only).
4. Review pregnancy prevention and continued use of barrier contraceptives with all subjects.
5. Obtain approximately 40 mL of blood for immunology (serum, plasma, PBMCs), PAXGene and virology* from serum and whole blood (PCR/culture). CBC will be done if prior white blood cell count (WBC), ANC, platelet count, or hemoglobin results are a Grade I or above and unresolved, as defined by protocol, on Study Day 16.
6. Obtain clean-catch urine for virus isolation (PCR/culture).
7. Obtain cervico-vaginal secretion or semen sample for virus isolation (PCR/culture). (Cervico-vaginal cup may be inserted at home by the volunteer prior to presentation to the clinic).
8. Obtain saliva sample for virus isolation (PCR/culture).
9. Obtain oral fluid for serology (CIR site only).
10. Review pregnancy prevention and continued use of barrier contraceptives.

*Whole blood/serum virology will be done only for those subjects who had detectable ZIKV in the blood at Study Day 16.

Study Day 28 (\pm 2 days from 28 days following test article administration)

1. Perform interim history, including sexual history, and focused physical exam, concentrating on any acute complaints.
2. Record vital signs.
3. Obtain approximately 50 mL of blood for immunology (serum, plasma, PBMCs), PAXGene and virology* from serum and whole blood (PCR/culture).
4. Obtain clean-catch urine for virus isolation* (PCR/culture).
5. Obtain cervico-vaginal secretion or semen sample for virus isolation* (PCR/culture). (Cervico-vaginal cup may be inserted at home by the volunteer prior to presentation to the clinic).
6. Obtain saliva sample for virus isolation* (PCR/culture).
7. Obtain oral fluid for serology (CIR site only).
8. Perform serum β -HCG testing (females only).
9. Review pregnancy prevention and continued use of barrier contraceptives.

*Whole blood/serum/CSV/semens/saliva/urine virology will be done only for those subjects who had detectable ZIKV in the blood at Study Day 21.

Study Day 35 (\pm 2 days from 35 days following test article administration)

1. Perform interim history, including sexual history, and focused physical exam, concentrating on any acute complaints.

2. Record vital signs.
3. Collect 8 mL blood for whole blood/serum virus isolation* (PCR/culture). Assays will be performed only for those subjects who had detectable ZIKV in the blood at Study Day 28.
4. Obtain clean-catch urine for virus isolation* (PCR/culture).

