5. Obtain cervico-vaginal secretion or semen sample for virus isolation* (PCR/culture). Cervico-vaginal cup may be inserted at home by the volunteer prior to presentation to the clinic).
6. Obtain saliva sample for virus isolation* (PCR/culture).
7. Perform serum β -HCG testing (females only).
8. Review pregnancy prevention and continued use of barrier contraceptives with all subjects.

*Whole blood/serum/CSV/semen/saliva/urine virology will be done only for those subjects who had detectable ZIKV in the blood at Study Day 28.

Study Day 56 (\pm 3 days from 56 days following test article administration)

1. Perform interim history, including sexual history, and focused physical exam, concentrating on any acute complaints.
2. Record vital signs.
3. Obtain approximately 40 mL of blood for immunology (serum, plasma, PBMCs)/serum virus isolation* (PCR/culture).
4. Collect 3 mL blood for whole blood virus isolation* (PCR/culture). Assays will be performed only for those subjects who had detectable ZIKV in the blood at Study Day 35 or 49.
5. Obtain clean-catch urine for virus isolation* (PCR/culture).
6. Obtain cervico-vaginal secretion or semen sample for virus isolation (PCR/culture)*. Cervico-vaginal cup may be inserted at home by the volunteer prior to presentation to the clinic).
7. Obtain saliva sample for virus isolation* (PCR/culture).
8. Obtain oral fluid for serology (CIR site only).
9. Perform serum β -HCG testing (females only).
10. Male volunteers: Review pregnancy prevention and continued use of barrier contraceptives.

*Whole blood/serum/CSV/semen/saliva/urine virology will be done only for those subjects who had detectable ZIKV in the blood at Study Day 49.

Study Day 70 (\pm 3 days from 70 days following test article administration)

1. Perform interim history for interim complaints. (Physical exam is optional).

2. Record vital signs.
3. Collect 8 mL blood for whole blood/serum virus isolation* (PCR/culture). Assays will be performed only for those subjects who had detectable ZIKV in the blood at Study Day 49 or 56.
4. Obtain clean-catch urine for virus isolation* (PCR/culture).
5. Obtain cervico-vaginal secretion or semen sample for virus isolation* (PCR/culture). (Cervico-vaginal cup may be inserted at home by the volunteer prior to presentation to the clinic).
6. Obtain saliva sample for virus isolation* (PCR/culture).
7. Obtain oral fluid for serology (CIR site only).
8. Perform serum β -HCG testing (females only).

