9. Male volunteers: Review pregnancy prevention and continued use of barrier contraceptives with all subjects.

*Whole blood/serum/CSV/semen/saliva/urine virology will be done only for those subjects who had detectable ZIKV in the blood at Study Day 56.

Study Day 90 (\pm 7 days from 90 days following test article administration)

1. Perform interim history for interim complaints. (Physical exam is optional).
2. Record vital signs.
3. Obtain approximately 40 mL of blood for immunology (serum, plasma, PBMCs)/serum virus isolation* (PCR/culture).
4. Collect 3 mL blood for whole blood virus isolation* (PCR/culture). Assays will be performed only for those subjects who had detectable ZIKV in the blood at Study Day 56 or 70.
5. Obtain clean-catch urine for virus isolation* (PCR/culture). Assays will be performed only if Day 56 or 70 sample was positive.
6. Obtain cervico-vaginal secretion or semen sample for virus isolation*. Assays will be performed only if Day 56 or 70 sample was positive. (Cervico-vaginal cup may be inserted at home by the volunteer prior to presentation to the clinic).
7. Obtain saliva sample for virus isolation* (PCR/culture). Assays will be performed only if Day 56 or 70 was positive.
8. Obtain oral fluid for serology (CIR site only).
9. Perform serum β -HCG testing (females only).
10. Review pregnancy prevention.

*Whole blood/serum/CSV/semen/saliva/urine virology will be done only for those subjects who had detectable ZIKV in the blood at Study Day 70.

Study Day 120 (\pm 10 days from 120 days following test article administration)

1. Perform interim history for interim complaints. (Physical exam is optional)

2. Record vital signs.
3. Collect 8 mL blood for whole blood/serum virus isolation* (PCR/culture). Assays will be performed only for those subjects who had detectable ZIKV in the blood at Study Day 70 or 90.
4. Obtain clean-catch urine for virus isolation (PCR/culture)*. Assays will be performed only if Day 70 or 90 sample was positive*.
5. Obtain cervico-vaginal secretion or semen sample for virus isolation* (PCR/culture). Assays will be performed only if Day 70 or 90 sample was positive. (Cervico-vaginal cup may be inserted at home by the volunteer prior to presentation to the clinic)*.
6. Obtain saliva sample for virus isolation* (PCR/culture). Assays will be performed only if Day 70 or 90 sample was positive.*
7. Perform serum β -HCG testing (females only).
8. Review pregnancy prevention.

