10.3.7.3 Mitigation of Risk of Transmission of ZIKV

To reduce the risk of ZIKV transmission, subjects will be housed in the inpatient unit from Study Day 0 through Study Day 9 (discharged on Study Day 9 if discharge criteria are met). ZIKV is generally able to be recovered from the blood for only a few days before and after ZIKV symptoms occur. A recent longitudinal study detected ZIKV by PCR in 88% of ZIKV-infected subjects [29]. ZIKV was detected in the serum at a level thought to be infectious ($C_T \leq 27$) only until approximately day 8 post-symptom onset. It is unlikely that infectious ZIKV will be detected in blood at a level that could be transmitted beyond Day 8 post-infection. Volunteers will not be discharged from unit unless the titer of ZIKV in serum, urine, saliva, cervico-vaginal secretions and semen is $< 1.4 \times 10^6$ genomic copies/mL by Study Day 8. At discharge from the inpatient unit, subjects will be given commercially available mosquito repellent containing DEET during mosquito season (May – October) and will be instructed to use it when outdoors through Study Day 28. In addition, this trial will be conducted as a dose-escalation study to ensure that only the lowest dose necessary to induce the desired virologic and clinical outcomes will be used. A very low dose of ZIKV (100 PFU) will first be evaluated. Lower doses of ZIKV are likely to induce lower titers in the blood and therefore reduce the risk of transmission. It is anticipated that the level of viremia induced in this study is below the level required for mosquito transmission ($\sim 3.0 \log_{10}$ PFU/mL). To reduce the risk of sexual transmission of ZIKV, subjects will be counseled on the use of barrier contraception through Study Day 56 (women) or Study Day 90 (men) and must agree to the use of barrier contraception when they engage in intercourse during this time period. Condoms will be provided to all subjects at no cost for the duration of the study. In addition, virus inoculum will be delivered by needle and syringe and is considered less infectious than natural mosquito-borne virus which is augmented by saliva factors.

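### Five visit footnotes make semen testing depend on virus in blood, against the protocol's own same-sample rule; secondarily, no specific rule acts on a late semen positive before Day 180

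*Combined protocol and SAP*

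**What the plan says.** **When semen is tested.** Section 6.4.1.2 lists semen without condition through Day 21. From Day 28, footnotes apply. Day 28: "semens/saliva/urine virology will be done only for those subjects who had detectable ZIKV in the blood at Study Day 21". Day 35: "semen/saliva/urine virology will be done only for those subjects who had detectable ZIKV in the blood at Study Day 28". Day 56: "semen/saliva/urine virology will be done only for those subjects who had detectable ZIKV in the blood at Study Day 49". Day 70: "semen/saliva/urine virology will be done only for those subjects who had detectable ZIKV in the blood at Study Day 56". The Day 90 footnote uses blood at Day 70 in the same way.

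The same section also states a different rule. Day 90 item 6 has semen assayed if the Day 56 or Day 70 sample was positive. The Note after the Day 180 list applies this logic to every sample type from Day 21: test if that sample was positive at an earlier time-point, and stop after two consecutive negatives. The Day 120 and Day 180 lists follow the same logic.

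Day 49 has no column in Table 1 and no procedure list. It is nevertheless named as a visit in the Precis (Study Design) and Section 7.2.1, and as a condition in Day 56 item 4, the Day 56 footnote and Day 70 item 3.

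**What follows a late positive.** Section 4.1 item 7 requires: "Male subjects: Willingness to use barrier contraception during cervico-vaginal, anal, and oral intercourse through Study Day 90". The last visit list to mention men's barrier use is Day 70: "Male volunteers: Review pregnancy prevention and continued use of barrier contraceptives with all subjects". Later contacts list only a pregnancy-prevention review. Semen positive at Day 90 or 120 leads to further sampling up to Day 180. Section 6.4.5 then provides follow-up until the fluid is clear and a prompt report, both tied to a Day 180 result: "Persistent shedding of Zika virus in bodily fluids at Study Day 180 will be reported to the DSMB and the FDA".

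**The concern.** Men were enrolled to learn how much infectious virus is shed in semen (Sections 1.1 and 4), and the quantity and duration of ZIKV in semen are part of Precis primary objective 2. Virus may persist in semen after blood is clear, so a rule that stops semen assays when blood clears cuts off the quantity being measured. It also disables Section 6.4.5. Day 180 semen is assayed only after a Day 90 or 120 positive, and Day 120 semen only after a Day 70 or 90 positive. If those earlier samples were never assayed, the Day 180 trigger has nothing to act on.

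If the same-sample rule is followed instead, a late positive is found and scheduled for resampling. No specific rule then uses the result to protect a partner before Day 180. The risk to a partner's fetus is one of the two major risks that the ethics consultation named (Section 1.1).

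**Working it through.** **1. The two rules side by side**

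| Semen visit | Footnote: assay if blood was positive at | Same-sample rule: assay if semen was positive at |
|---|---|---|
| Day 28 | Day 21 | an earlier time-point (Note) |
| Day 35 | Day 28 | an earlier time-point (Note) |
| Day 56 | Day 49 (no procedure list) | an earlier time-point (Note) |
| Day 70 | Day 56 | an earlier time-point (Note) |
| Day 90 | Day 70 | Day 56 or 70 (item 6) |

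A man with clear blood and positive semen gets opposite answers in every row. The blood conditions also form a chain. Day 21 blood is assayed only if Day 16 blood was positive, Day 28 blood only if Day 21 was positive, and so on. Under the footnotes, a negative blood result therefore closes semen testing for good. Read literally, the Day 56 condition cannot be met, because no Day 49 blood draw is listed.

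**2. When blood clears**

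- ZIKV-SJRP, Table 5, whole-blood PCR: mean onset Day 4.2, longest duration 15 days. Last positive day from the mean onset: 4.2 + 15 - 1 = 18.2, or 4.2 + 15 = 19.2. Both precede Day 21. An onset at Day 7 with a 15-day run would just reach Day 21 (7 + 15 - 1 = 21).
- ZIKV-Nicaragua, Table 7, serum PCR (the extracted columns are displaced; read as mean onset 2.4 and mean duration 11.4 days): 2.4 + 11.4 - 1 = 12.8 to 2.4 + 11.4 = 13.8. No range is given, so clearance by Day 21 is likely on average but not shown for every man.

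For comparison, Section 1.1 cites semen RNA for 2-6 months after symptoms and infectious virus up to 69 days after onset.

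**3. Men and assays involved.** Cohorts 3 and 4 include 20 ZIKV men. Ever RT-PCR positive in semen, from the two cited studies: 20 x 60/184 = 6.5 and 20 x 32/97 = 6.6. Ever infectious, from the second study: 20 x 8/97 = 1.6. The 6.5% infectious rate in the first study is not scaled, because its denominator is not given.

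Assays added by the same-sample rule at Days 28, 35, 56, 70 and 90: 6.6 x 5 = 33 if every RNA-positive man stayed positive throughout. The ceiling is 20 x 5 = 100.

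**4. Time from a late positive to the Day 180 trigger**

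- From Day 90: 180 - 90 = 90 days. With windows: (180 - 14) - (90 + 7) = 69 to (180 + 14) - (90 - 7) = 111.
- The 111 days start at a Day 83 visit, when the barrier requirement still has 7 days to run. The most that can fall after it ends is 194 - 90 = 104 days.
- From Day 120: 60 days, with windows 166 - 130 = 36 to 194 - 110 = 84.

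**5. How likely is a late positive?** The documents give no semen-positive rate at Day 90 or 120. If 1%, 2%, 5% or 10% of ZIKV men were positive then (assumed values), the chance of at least one among 20, 1 - (1 - p)^20, is 18%, 33%, 64% or 88%. Most such positives would probably be RNA only. In the first study 0 of 59 samples from after day 30 of illness grew virus, a one-sided 95% upper limit of 1 - 0.05^(1/59) = 5.0% per sample if samples are independent.

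**The case against.** The case for the plan is strongest on the late positive. Day 90 follows the CDC guidance cited in Sections 4 and 4.1, and it exceeds the 69-day longest recovery of infectious virus. The protocol knew that RNA persists for months and chose a limit based on infectious virus. The DSMB meets twice a year and may convene extra reviews (Section 7.6.3). An unanticipated-problem report is possible, and the Safety Review and Communications Plan, which is not available here, may add more. Condoms stay free, and pregnancy prevention is reviewed through Day 180.

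All of this stands. A reader might infer that the plan knowingly releases infectious men, or that nothing at all happens before Day 180. The documents support neither. What remains is narrower: no specific, prompt rule exists. The unanticipated-problem route needs an unexpected event, which described RNA persistence would hardly be, and a problem that is not an adverse event does not go to the sponsor's safety office (Section 7.3.3).

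On semen testing, the same-sample rule is already in the text, so this may be only a drafting conflict. Semen is collected from all men through Day 90 and specimens are stored (Section 8.3), so unassayed samples could be tested later. It would therefore be too strong to say that the data are lost. But no such retesting is planned, and samples after Day 90 are collected only on earlier results or when results are unavailable.

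The two consequences also cannot both apply in full. Under the footnotes a late positive is rarely found; under the Note it is found and not acted on.

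**Conclusion.** The footnotes are an error in the text and should be corrected. They contradict Day 90 item 6 and the Note. If followed, they would usually end semen assays after Day 21, so the scheduled assays could not measure duration of shedding in semen. That expectation assumes that men clear blood much as the women in cohorts 1 and 2 did. The Precis expects similar replication kinetics by sex. The evidence is firmer for ZIKV-SJRP than for ZIKV-Nicaragua, where only a mean duration from five recipients is available.

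The missing rule for a semen positive at Day 90 or 120 is a cheap safety improvement, not an error. The probability of harm is low and its severity for a fetus is high. The interval is 90 days by schedule from a Day 90 positive, with at most 104 days after the barrier requirement ends. The number of men affected cannot be estimated from the documents.

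**What to change.** **Semen testing.** In the Day 28, 35, 56, 70 and 90 footnotes, make testing of each fluid depend on that fluid's own earlier results, as in the Note. Remove or reconcile every Day 49 reference: Precis (Study Design), Section 7.2.1, Day 56 item 4 and footnote, and Day 70 item 3. The semen is already collected, so no visits are added. The cost is about 33 semen assays if natural-infection rates apply and at most 100, plus saliva and urine assays not counted here.

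**Late positives.** Extend the Section 6.4.5 DSMB/FDA report to any semen positive at Day 90 or 120. Review barrier use with all men at Day 90, which discloses nothing about assignment. Ask a man whose latest semen result is positive, once the result is available and his block is unblinded, to continue barrier use until one of these holds:

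- two consecutive semen samples are negative;
- the sample is at or below 1.4 x 10^6 copies/mL or shown to be non-infectious (the Section 6.4.2 item 4 standard, where either condition suffices);
- the DSMB or FDA advises otherwise.

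Make matching edits in the Precis safety items, Section 4, 4.1 item 7, 6.3 item 14, 10.3, 10.3.6.4 (which gives Day 56 for all subjects), 10.3.7.1 and 10.3.7.3.

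This costs a short amendment with IRB approval, a consent revision, and longer barrier use for a few men. Under the two-negatives criterion that lasts to about Day 180, because semen is next scheduled at Days 120 and 180; a low-titer man is released sooner. A short gap can remain while a result or the block's unblinding is pending.
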